#### Project Timeline:

The equipment and resources are currently in place to begin patient examinations immediately upon receiving funding. We anticipate the recruitment of all 100 patients from the existing pool of patients at the Emory Clinics (Survivorship Clinic) within the 12 months of funding. The time from baseline MRI and initial follow-up MRI study will be 18 months which would give us time to observe therapy related changes in the plaque morphology and inflammation, observe correlation between plaque inflammation and inflammatory markers in the serum and also with

cardiac functional status as assessed by echocardiography and CT. The 2nd set of follow up MRI and blood tests at 36 months would serve as the end point for final analyses of the long term effects of the instituted treatment regimen. Thus, if the co-investigators responsible for statistical models receive the complete data 3 months after the end of the studies, it is expected to take another 3 months to complete the entire work. So realistically the project should be completed in 39 months.

**Adverse Event Reporting:**

We do not expect any serious physical adverse events from this research study. Participating in this study involves very few/minimal risks. Study staff will work with patients to minimize any stress or discomfort with the study procedures. The study involves a blood draw, which may cause slight bruising or pain at the site where the blood is drawn. In addition, bleeding, dizziness, fainting or feeling lightheaded, nausea, hematoma or infection may occur because of drawing your blood. The blood will be drawn from expert/trained staff so this will be less likely to happen.

The Computed Tomography (CT) for coronary artery calcification (CAC) and Echocardiogram are both non-invasive procedures. CT exams are generally painless, fast and easy. The risks associated with CAC screening are small (48). The echocardiogram is very safe, painless and uses ultrasound waves, for which there are no known risks.

We do not expect any serious physical adverse events from MRI examinations. Due to recent concerns related to the use of gadolinium-based contrast agents in patients with renal dysfunction and risk of nephrogenic systemic fibrosis (NSF), serum creatinine levels will be measured from blood drawn before each MRI examination (49). Patients with normal renal function values will be administered contrast and this approach virtually eliminates any possibility of NSF.

Statin treatment might cause some side effects in few individuals which would be closely monitored by symptoms and followed by blood tests; if any side effects occur, the medication would be immediately stopped; patients would be taken off the study protocol and they would continue their routine follow up in The Survivorship and Cardiology clinics.

Subjects will be provided with telephone numbers of the PI, co-investigators and the Emory University IRB. Any adverse events will be appropriately documented and reported through the Department of Radiology Safety Committee.

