## Aims

The purpose of this study is to assess carotid artery MRI plaque characteristics in 100 asymptomatic cancer survivors with history of chest, head and neck radiotherapy (HNXRT) and with subclinical atherosclerosis. Another objective is to analyze plaque changes in the same group after initiation of medical treatment for 18 and 36 months.

The following specific aims (A), research questions (RQ) and hypotheses (H) will be addressed.

A 1: To characterize the plaque constituents including fibrous cap (FC), lipid core and hemorrhage within the carotid plaque by MRI

RQ 1a: What are the predominant plaque constituents?

RQ 1b: Is there a predominance of complex and vulnerable plaque features in the neck arterial vasculature of cancer survivors?

H 1: We hypothesize that there is a predominance of vulnerable plaque in carotid arterial vasculature of HNXRT patients due to the phenomenon of radiation vasculopathy.

A 2: Determine the correlation between plaque inflammation (direct measure by MRI) with serum markers of inflammation through blood tests (hsCRP, LpPLA2, IL-6) and metabolomics

and other tests of cardiac or vascular dysfunction (echocardiography and computerized tomography coronary calcium score studies).

RQ 2: Is there any correlation between the direct and surrogate markers of inflammation?

H 2: We hypothesize that there is a predictable correlation between the direct and surrogate measures of inflammation.

A 3: To assess the longitudinal change in the artery plaque characteristics (inflammation and morphology) with treatment.

RQ 3: Is there a predictable relationship between inflammation (pattern of enhancement-contrast kinetics) and vulnerable features within a plaque?

H 3: We hypothesize that changes in plaque characteristics pre and post treatment would correlate with contrast agent dynamics over time.

A 4: To determine the efficacy of comprehensive treatment (life style modification + statin) versus (life style modification + placebo).

RQ 4: Is one regimen better than the other in cancer survivors with subclinical atherosclerosis?

H 4: We hypothesize that comprehensive treatment (life style modification + statin) would have better inflammation control and favorable plaque modification than life style modification alone as measured by parameters in (A2 & A3).

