#### **Examination Plan Overview:**

All participants will be given IRB approved informed consent. Those who decide to take part and give consent for the study would be enrolled in the research study. We would be taking snap shots with MRI at three data points and monitor treatment effects. Overview of the research study is shown in Fig 2. A baseline MRI will be performed to assess arterial atherosclerotic constituents. Once the initial MRI has been performed, and in the case where subclinical disease is present i.e. elevated blood markers or arterial plaque on MRI. HNXRT cancer survivor patient with abnormal tests will be started on treatment, which includes life style modification and-/or lipid lowering medication. Patients with positive tests would be divided randomly into two groups; one group will receive life style modification + statin therapy and the second group will receive life style modification alone. A repeat MRI and blood tests (2nd study) will be performed at 18 months after initiation of such treatment to assess changes in plaque morphology and enhancement characteristics. MRI findings of baseline and final would be

correlated with surrogate markers of inflammation, Echo and CT findings. A final set of MRI and blood tests will be performed at 36 months after initiation of such treatment to assess changes in plaque morphology and enhancement characteristics. MRI findings of baseline and final would be correlated with surrogate markers of inflammation, Echo and CT findings.

Fig 2. Shows overview of the research study

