#### Treatment and Clinical Follow-Up:

Patients enrolled in the “Accelerated Atherosclerosis in High Risk Population Groups: An Assessment by Magnetic Resonance Imaging” study will be evaluated in the cardiology clinic by [name],

FACC, FSCAI who is the Director of Peripheral Vascular Intervention at Emory University and treats patients with carotid artery disease. All these patients will be randomized based on the last digit of their medical record number. If the last digit will be an even number they will then be given a statin, which they will take and will also be instructed about regular exercise. Patients will be made aware of the side effects of statins and about the procedures to report these side effects. Patients with the last digit being an odd number will ONLY be advised about exercise. All patients will have regular visits and patients on a statin will be followed up and evaluated for any adverse effects of the medication and for compliance at 18 and 36 months by the study preventive cardiologist. The preventive cardiologist or any other physician involved with care of the patient may elect for more frequent follow up as well as modification or discontinuation of the study prescribed therapy if deemed necessary based on his or her best clinical judgment.

These patients will get routine clinical follow-up in the oncology (The Winship Cancer Institute Clinics) and cardiology clinics (Emory Hospital) as part of the ongoing routine clinical care.

Within five weeks of initial MRI evaluation, our recruited research that demonstrate increased blood markers and/or atherosclerosis on MRI would be subjected to life style modification ± medical (statin) therapy. Department of Cardiology would prescribe and monitor statin therapy: Rosuva (20 mg once a day) with target LDL goal < 70; non-HDL goal < 100 and Aspirin (81 mg once a day). The rational for using rosuva 20 mg is because this dosage has already been successfully used in JUPITER Trial (35). The follow-up by Cardiology department would comprise educating the patients on life style modification and also how to monitor and report any adverse drug affects which if expected would be further assessed with laboratory testing with LFT's and CBC. Any patients who suffer clinical side effects of treatment as part of our research would be taken off our study. Patients will continue to follow-up in the survivorship clinic and with the preventative cardiologist as indicated.

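### Patients with statin side effects are taken off the study, so the Aim 4 comparison loses follow-up mainly from the statin arm

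*Combined protocol and SAP*

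**What the plan says.** Two sections link a side effect to leaving the study. Under Adverse Event Reporting, "if any side effects occur, the medication would be immediately stopped; patients would be taken off the study protocol", and then "they would continue their routine follow up in The Survivorship and Cardiology clinics". Under Treatment and Clinical Follow-Up, "Any patients who suffer clinical side effects of treatment as part of our research would be taken off our study".

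The arms differ in exposure to this rule. The Examination Plan Overview says that "one group will receive life style modification + statin therapy and the second group will receive life style modification alone". Treatment and Clinical Follow-Up says that patients on a statin "will be followed up and evaluated for any adverse effects of the medication and for compliance at 18 and 36 months". On frequency, the only statement is that "Statin treatment might cause some side effects in few individuals".

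Aim 4 asks: "Is one regimen better than the other in cancer survivors with subclinical atherosclerosis"? According to the Project Timeline, "The 2nd set of follow up MRI and blood tests at 36 months would serve as the end point for final analyses". The Aim 4 data analysis paragraph says that the methods of Aims 1 to 3 will be combined and fitted with SAS PROC MIXED. It names no analysis set and no rule for patients removed after a side effect.

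**The concern.** Stopping a drug and stopping measurement are separate decisions, and the plan merges them. A patient removed before 18 months contributes only baseline data to Aim 4. One removed between 18 and 36 months contributes the 18-month visit but not the 36-month end point. Because the trigger is mainly a statin side effect, the loss falls mainly on one arm and is selected by tolerability.

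Two things are then at stake.

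- **What is estimated.** The comparison becomes statin-tolerant patients against everyone given lifestyle modification alone. A mixed model with arm and time terms would estimate roughly the effect had removed patients stayed on the drug. That is a legitimate target, but the plan does not choose it, and it is not the effect of the allocated regimen.
- **Bias.** If removed patients would have had a different plaque course from retained patients for other reasons, the comparison is biased even for that target.

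Outcomes that are never collected cannot be recovered at the analysis stage.

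**Working it through.** **The plan's own figures.** The Sample Size section gives none for Aim 4. Its Aim 3 figure does reproduce: a one-way ANOVA with three measurements, effect size 0.28, 92 per measurement and alpha 0.05 has power 0.990. It does not bear on a comparison between arms. The attrition allowance of about 10% is not split by arm or by cause.

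**Assumptions, since the documents give no side-effect rate.** There are 50 patients per arm (100 split about evenly by record-number digit). A proportion p = 0.04, 0.10 or 0.20 of the statin arm is removed, that is 50p = 2, 5 or 10 patients. Removal occurs before the 18-month MRI unless stated, and there is no other loss. A two-sample t-test on change stands in for the mixed model, without covariates.

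**1. Gap between the two targets.** Let the on-drug effect be δ, and let stopped patients change like controls. The allocated-regimen effect is (1 − p)δ and the remaining-patient effect is δ. Their ratio is 1/(1 − p):

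- p = 0.04: 1/0.96 = 1.042
- p = 0.10: 1/0.90 = 1.111
- p = 0.20: 1/0.80 = 1.250

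**2. Bias when there is no treatment effect.** Suppose retained patients change more favourably than removed ones by d = 0.5 SD. The whole statin arm has mean zero, so (1 − p)·m + p·(m − d) = 0, where m is the retained mean. This gives m = p·d, which is the bias. The type I error is that of a two-sided 5% t-test with 50(1 − p) against 50 patients and a true shift of p·d.

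| p | n statin v control | Bias (SD) | Type I error, noncentral t | Type I error, 400,000 simulations |
|---|---|---|---|---|
| 0.04 | 48 v 50 | 0.02 | 5.11% | 5.15% |
| 0.10 | 45 v 50 | 0.05 | 5.67% | 5.65% |
| 0.20 | 40 v 50 | 0.10 | 7.53% | 7.53% |

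With d = 0 there is no bias and the error is 5%. With d of the opposite sign, the bias runs against the statin.

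**3. Later removal.** If all removals follow the 18-month MRI, the 18-month comparison is complete and unbiased in case 2. At 36 months a likelihood-based model uses the 18-month value to correct by ρ·p·d, leaving p·d·(1 − ρ). With an assumed correlation ρ = 0.5 between 18- and 36-month change, the remaining bias is 0.010, 0.025 or 0.050 SD.

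**4. Power under each approach.** Take an on-drug effect of 0.6 SD, a two-sided 5% test and the noncentral t. If stopped patients change like controls, the allocated-arm effect is 0.6(1 − p) = 0.576, 0.54 or 0.48 SD.

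| p | Allocated arm, all followed (50 v 50) | Remaining patients only |
|---|---|---|
| 0.04 | 81.4% | 83.6% (48 v 50) |
| 0.10 | 76.2% | 82.4% (45 v 50) |
| 0.20 | 66.1% | 79.9% (40 v 50) |

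**The case against.** The case on the other side is mostly about size.

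- **Frequency.** The plan expects side effects in few patients. At 4% or 10% removal the type I error barely moves, and the 20% case fits poorly with that expectation. The 0.5 SD difference and its direction have no support in the documents. This stands: the size is unknown and may be small.
- **Timing.** Adverse effects are formally evaluated at 18 and 36 months, so removals prompted by those visits could follow a scan, and the bias is then smaller (step 3). But patients are also told how to report side effects at other times, so early removal remains possible.
- **Target.** The excess in step 1 is a difference between two targets, not bias, and Aim 4's efficacy wording is compatible with an on-drug target. This also stands. The gap is that the plan makes no choice and discards the data needed for the alternative.
- **Model.** The plan writes out no Aim 4 model, and the model given for Aim 3 has no arm term. What would be estimated is therefore an inference.
- **Not only one arm, not every stop.** Side effects of treatment could include exercise harms. It is not clear that aspirin is limited to one arm, and the Aims section mentions a placebo. Physicians may also modify or stop therapy without the text saying that the patient leaves. These points make the loss predominantly, not exclusively, in the statin arm. They do not override the two removal sentences.
- **Off protocol may mean off drug only.** The Adverse Event Reporting wording alone could be read so. The Treatment and Clinical Follow-Up sentence and the return to routine care point to leaving the study.

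The mixed model is a partial defence. It keeps visits made before removal and is valid if data are missing at random, but it cannot supply off-drug outcomes that were never measured.

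**Conclusion.** The concern holds. Followed as written, the plan loses Aim 4 end-point data mainly from the statin arm, selected by tolerability, and it neither chooses an on-drug target nor says how removed patients are handled. That conclusion rests on the text alone.

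The size rests on assumptions. For 4% to 20% early removal, the remaining-patient contrast exceeds the allocated-regimen effect by 4% to 25% if stopped patients change like controls. Type I error rises to between 5.1% and 7.5% if retained and removed patients differ by 0.5 SD. It does not rise if they do not differ, and the bias is smaller if removals come after the 18-month scan. The plan should be changed because the remedy is cheap and the lost data cannot be recovered, not because a large bias has been shown. Confidence is medium.

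**What to change.** Leave the drug-stopping rule and physician discretion as they are. In Treatment and Clinical Follow-Up and in Adverse Event Reporting, replace the off-study wording with:

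*Patients who have side effects of study treatment, or who stop the statin, remain in the planned 18- and 36-month MRI and blood follow-up unless they withdraw consent or MRI or contrast becomes contraindicated.*

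In the Aim 4 data analysis paragraph, add:

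*Aim 4 is analysed by allocated arm using all measurements, including those after stopping; stops are reported by arm, date and reason.*

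An on-drug analysis can still be reported beside it, and a sensitivity analysis for patients who are nevertheless lost would be a sensible addition.

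The cost is a protocol amendment with matching consent wording. At the assumed rates, 2, 5 or 10 patients stay in follow-up, at most 2 × 50p = 4, 10 or 20 visits, all among the 100 × 2 = 200 follow-up visits already planned. The downside is power. If stopped patients change like controls, the allocated-arm analysis has about 81%, 76% or 66% power for a 0.6 SD on-drug effect, against 84%, 82% or 80% among remaining patients only. With the plan's 10% attrition (45 per arm), the allocated-arm figures are about 77%, 72% and 61%.
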